#### 8.1.1 B-symptoms

B-symptoms are constitutional symptoms defined as any one or more of the following disease-related symptoms or signs:

- Unintentional weight loss of 10% or more within the previous 6 months,
- Fevers > 100.5°F or 38.0°C for  $\ge$  2 weeks without other evidence of infection, or
- Night sweats for > 1 month without evidence of infection.

B-symptoms should not be reported as AEs and will be collected when a disease response assessment is performed during treatment and as clinically indicated.

The presence of B-symptoms should not be used in the overall response assessment as per Lugano 2014 criteria. In fact, the presence of residual symptoms in the absence of detectable disease by imaging does not preclude the designation of complete response.

#### 8.1.2 Efficacy Assessment Types

All efficacy assessments captured at baseline and during the study will include the following evaluations: Physical examination and imaging by PET-CT scan (preferred modality).

#### **Physical Examination**

Lesions detected by physical examination will only be considered measurable if superficial, eg, skin nodules, and palpable lymph nodes and spleen. Documentation by color photography including ruler is recommended for estimating the size of skin lesions and photographic documentation should be submitted to BICR and kept in medical records. Unless unequivocally related to lymphoma, new or worsened abnormalities should be reported as AE.

#### Radiological Assessments

Imaging is required for all participants, PET, and contrast CT scans to be performed as indicated in the SoA and in Table 16. If the study treatment is discontinued prior to PD, participant in response PR or CR (including participant in CR who received radiotherapy with consolidation intent) or stable disease will continue to be monitored for efficacy until PD, death, start of a new anti-cHL treatment, whichever comes first as per Table 16. If the treatment is discontinued prior to Year 1, the timepoints for disease assessment should follow approximately those of regular treatment administration.

**Note:** participant in CR/PR who proceeds to HSCT without any treatment between the last dose of sabestomig and the start of the conditioning regimen will be followed-up for disease assessment post-transplant as per SoC and data on their disease status will be collected in the EDC as part of the survival follow-up.

#### Table 16Radiology Scans for Tumor Assessments

Time	points	Radiologic Scans a		
Screening		Contrast CT	PET	
During the study b		Contrast CT	PET	
	CCI	Contrast CT	PET	

Timepoints		Radiologic Scans a		
	CCI	Contrast CT	PET	
	Year c 1	Contrast CT	PET	
	Q6M until EoS °	Contrast CT	PET	

Disease response should be assessed by PET-CT as per Modified Lugano criteria (2014) until participant achieves CR. Once CR is achieved, contrast CT may replace PET-CT until PD is suspected. If PD is suspected, PD must be confirmed by PET scan.

b At least 10 days post infusion, but prior to the next infusion.

c Calculated from the time of first dose ( $\pm 2$  weeks).

Abbreviations: CT computed tomography; EoS: end of study; PD: progressive disease; PET-CT: positron emission tomography-CT.

Imaging modalities selected at baseline should remain consistent during the study; participants should have imaging assessments done at the participating study center or an acceptable alternate imaging facility using an identical imaging protocol and similar equipment.

The following options can be used:

- If PET-CT is of diagnostic quality with contrast, a separate CT/MRI with contrast is not required.
- If PET-CT is of diagnostic quality BUT without contrast, a separate CT/MRI with contrast is preferred but not mandatory.
- If PET-CT is not of diagnostic quality, a separate diagnostic-quality CT should be performed per SoC practices. In the event of contrast shortage, if a change in modality from CT to MRI is necessary, consider following the participant with MRI at least until the shortage is over.

Note: Diagnostic quality CT means that acquisition parameters, such as tube current, voltage, and exposure, of CT portion of PET are similar/comparable to a routine abdominal/pelvic CT scan done for diagnostic purposes, as per site's SoC.

Brain MRI or brain CT with contrast (if possible) will be performed at baseline only if there is a prior history of CNS involvement or if there are neurologic signs or symptoms present and as clinically indicated during the study.

- CT scans:
  - CT scans should be performed with contiguous cuts in slice thickness of 5 mm or less. Spiral CT should be performed using a 5-mm contiguous reconstruction algorithm.
  - The CT scans should cover the neck, chest, abdomen, and pelvis and any other disease sites as clinically indicated.
  - If the use of CT IV contrast is clinically contraindicated or frequent contrast CT scans are not allowed by the local IRB/Ethics Committee, an MRI may be used for

imaging assessments. In cases where MRI is desirable, the MRI must be obtained at screening and at all subsequent response-evaluations.

- Disease response should be assessed by PET-CT as per Modified Lugano criteria (2014) until participant achieves CR.
- For all participants who achieve CR, a CT with contrast may replace PET-CT to monitor disease response until PD is suspected. If PD suspected, PD must be confirmed by PET.
- If PET and CT scans are performed on the same day, PET must be performed prior to contrast-enhanced CT.
- For participants who require both a CT with contrast and a PET together, a CT without contrast is permissible during the Investigator assessed response period (Part A only) provided that the institution can provide accurate measurement without contrast for the CT portion per the Investigator.
- MRI scans:
  - MRI scan is acceptable for measurement of lesions provided that the same anatomical plane is used for serial assessments. If possible, the same imaging device should be used for serial evaluations.
- PET:
  - The PET scans should cover the whole body from base of skull to mid-thigh. The visual interpretation of PET scans will be performed using the 5-point scale Deauville criteria (Appendix C 2). Target lesions selected at baseline (max 6) must meet the measurability criteria and show FDG-avid uptake. Lesions visible on PET but not measurable on CT/MRI should be assigned as non-target lesions. Refer to Appendix C Lugano for additional details.

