#### **Intervention Groups and Duration:**

Following an initial screening period of up to 4 weeks, eligible participants will receive sabestomig every 3 weeks (Q3W) administered via intravenous infusion at the selected dose starting on Cycle 1 Day 1. Participants will be treated with study intervention for a maximum of 35 cycles, or until disease progression, unacceptable toxicity, withdrawal of consent, or if other reasons to discontinue treatment occur. All participants will be followed for survival until the end of study, regardless of whether treatment was discontinued.

No dose reductions of sabestomig will be allowed. Dose modification (hold or delay) and toxicity management for sabestomig-related toxicity, including management of immune-mediated reactions, infusion-related reactions, and non-immune-mediated reactions are provided in the Toxicity Management Guidelines (Appendix I).

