#### Table 3Schedule of Activities for the Intervention Period (Part B Dose Expansion)

Table 3	Schedule of Activities for the Intervention Period (	(Part B Dose Expansion)

Study Period	Intervention Period					
Visit	V2	V3	V4	V5	V6	V7-Vn
Cycle Number and Day	C1D1	C1D8	C1D15	C2D1	C2D8	C3D1-CnD1
Procedure/Window		± 1 D	± 3 D	± 1 D	± 3 D	± 3 D
Disease Assessments						
Imaging disease assessment (Section 8.1, Table 16) t	At least 10 days after sabestomig administration in Cycle and then thereafter at Year 1 from the date of the first infusion, then Q6M until PD, start of new treatment for HL or EoS (whichever occurs first). Of Note: if a participant in CR receives RT as consolidation, imaging disease assessment should continue until the participant meet the criteria mentioned in the paragraph above.					

a On dosing days, the physical examination will be conducted prior to sabestomig administration.

b All ECGs will be obtained in triplicate (all within a 5-minute time period). Collection times for ECGs on days of sabestomig administration are shown below. Whenever ECGs and blood draws (eg, PK/ADA) are scheduled for the same nominal time, the blood draws should occur last. The timing of the ECG should be such that it allows the blood draw to occur at the proper nominal time. Day 8 assessment only to be performed if cardiac signal is detected in Part A.

Collection Times for ECGs on Sabestomig Dosing Days						
Cycle Number and DayPrior to SOI (within 30 mins prior to SOI)1 h (± 5 mins) Post EOI						
C1D1, C2D1, C3D1, and C4D1	Х	Х				
C5D1, C6D1, etc.	As clinically indicated					

c If clinically indicated, and at the Investigator's discretion, a consultation with a cardiologist is recommended for follow-up.

d Collection times for vital signs and pulse oximetry on days of sabestomig administration are shown below. Whenever vital signs and blood draws (eg, PK/ADA) are scheduled for the same nominal time, the blood draws should occur last. The timing of the vital signs assessment should be such that it allows the blood draw to occur at the proper nominal time.

Collection Times for Vital Signs and Pulse Oximetry on Sabestomig Dosing Days						
Cycle Number and Day	Prior to SOI (within 30 mins prior to SOI)	EOI (± 5 min)	30 mins (± 10 min) Post EOI			
C1D1	Х	Х	Х			
C2D1, C3D1, C4D1, etc.	Х		Х			

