## 6.7 Dose Delay

In the event of treatment-related toxicities, study intervention should be permanently discontinued if sabestomig is not given for more than 12 weeks.

If treatment interruption is caused by intercurrent illness that is not a direct consequence of sabestomig-related toxicity (ie, COVID-19 infection), the option to restart treatment can be offered beyond 12 weeks following discussion with the AstraZeneca representative. In the event of a COVID-19 infection, the investigator should use their judgment to delay treatment with sabestomig depending on the clinical situation of the participant.

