# 9.3 **Populations for Analyses**

For purposes of analysis, the study populations are defined as provided in Table 21. For the safety and PK analyses, participants will be classified according to the dose level they actually received. For all efficacy analyses, and for baseline and demography, participants will be classified according to the dose they were assigned to (ie, the planned treatment/dose level/dose schedule).

Population/Analysis set	Description	Endpoint/Output
Enrolled	All participants who sign the Informed Consent Form, or whose legally authorized representative a sign the Informed Consent Form.	Disposition
Full / Safety	All participants who received any amount of study intervention	Exposure Safety Baseline and demography PFS OS
Interim safety	All participants who received the first dose at least 6 weeks prior to data cut-off	Safety at interim
DLT-evaluable	Participants enrolled in the dose escalation phase who have received sabestomig and completed the DLT evaluation period (defined as 28 days after the start of study intervention) or who experience any DLT	DLT
Response-evaluable	All dosed participants who had measurable disease at baseline	ORR CRR BOR Duration of response Duration of complete response
Interim response-evaluable	All dosed participants who had measurable disease at baseline and received first dose at least 10 weeks prior to data cut-off	Efficacy at interim
РК	All participants who received at least 1 dose of study intervention with at least 1 reportable concentration	PK concentrations PK parameters
Pharmacodynamics	All participants who received at least 1 dose of study intervention with at least 1 reportable pharmacodynamic measurement	Pharmacodynamic endpoints
Immunogenicity	All participants who received at least 1 dose of study intervention with at least 1 reportable immunogenicity measurement	
Exploratory biomarkers	All participants that participate in the exploratory biomarker research	Biomarker endpoints

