#### List of Substantial Modifications

Section # and Name	Description of Change	Brief Rationale
		half lives have shorter washout
		periods.
Section 6.1.1 Investigational	Added description of CCI formulation.	New CCI formulation added.
Products – Table 10, and		
Section 6.1.2 Identity of		
Investigational Product(s)		
Section 6.2.1 AZD7789	Added preparation and administration	New CCI formulation added.
Infusion Preparation and	guidance for CCI formulation.	
Administration		
Section 8.1.4 Patient-	Added description of quality of life / PRO	To acquire additional information
Reported Outcomes, Section	secondary and exploratory endpoints to	regarding the impact of AZD7789
9.4.3 Safety Analyses, and	be included in Part B of study.	on PRO to support development
Section 9.4.4.4 Patient-		of therapy for r/r cHL population.
Reported Outcomes		
cHL: classical Hodgkin Lymphoma; CCI		
; CC I		; imAE: immune-
mediated adverse event; PD-1: programmed cell death protein-1; PD-L1: programmed cell death ligand-1; r/r:		
relapsed or refractory; Peds: Pediatric; PGI-TT: Patient Global Impression of Treatment Tolerability; CCI:		
CCI	; CCI	; PRO: patient-
reported outcomes: PRO-CTC	AF. Patient-Reported Outcomes version of t	he Common Terminology Criteria

reported outcomes; PRO-CTCAE: Patient-Reported Outcomes version of the Common Terminology Criteria for Adverse Events.

List of Non-substantial	I Modifications
-------------------------	------------------------

Section # and Name	Description of Change	Brief Rationale
Throughout	Administrative change: The version numbering was updated. Typos were corrected and minor clarifications made.	Editorial updates
Title Page	Added EU CT number	Update required to comply with EU CTR.
Section 1.1 Synopsis, and Section 9.3 Populations for Analyses – Table 21	Updated definition of interim response-evaluable population.	Update to be in consistent with planned response assessment for Cycle 3.
Section 1.3 Schedule of Activities – Table 1	COVID-19 testing added to screening procedures and footnote added.	COVID testing is required at screening per eligibility criteria; updating SoA to align.
Section 1.3 Schedule of Activities – Tables 1, 2, 3	Moved biomarker evaluation for Genomics Initiative from Screening to Cycle 1 Day 1	Participants must fulfill eligibility criteria for inclusion in the genetic research

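### First-year scans follow dosing cycles but the interim futility set follows calendar weeks, so a participant with a long early dose hold can enter a futility look before any scan is due

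*Protocol*

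**What the plan says.** **Scan timing.** The Part B schedule (Protocol Table 3) sets imaging "At least 10 days after sabestomig administration in Cycle and then thereafter at Year 1 from the date of the first infusion"; the cycle numbers are blacked out. Tables 2 and 4 follow the same pattern. Footnote b of Table 16 gives the on-study window as "At least 10 days post infusion, but prior to the next infusion". Only the Year 1 and six-monthly scans are on the calendar; footnote c has them "Calculated from the time of first dose", within 2 weeks either way.

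**Interim set.** Protocol Table 21 defines the interim response-evaluable set as "All dosed participants who had measurable disease at baseline and received first dose at least 10 weeks prior to data cut-off". Section 9.5 and SAP Section 5 judge futility on this set. The Version 4 change table in Appendix L gives the reason for its definition: "Update to be in consistent with planned response assessment for Cycle 3".

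**Delays.** Section 6.7 says that after treatment-related toxicity "study intervention should be permanently discontinued if sabestomig is not given for more than 12 weeks", so shorter gaps can end in resumed dosing. Section 8.1.2 protects the scan calendar in one situation only: "If the treatment is discontinued prior to Year 1, the timepoints for disease assessment should follow approximately those of regular treatment administration". No section says when to scan while dosing is on hold. SAP Section 3.3.2 re-anchors visits after a cycle delay, but lists this only under safety assessments. For tumor assessments it uses the protocol windows, and SAP Appendix B 1 sends any scan outside its study-day windows to an unscheduled timepoint.

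**The concern.** The scan schedule and the interim set run on different clocks. The change log shows that they were meant to agree, and they do so only when dosing is on time. A delay before the Cycle 3 infusion moves the scan but not the date of entry to the futility denominator. A participant can then be counted with no scan due and, absent an unscheduled scan, with no possibility of a recorded response.

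The error is tied to toxicity rather than random, and it pushes towards a false No-Go. Section 9.2 says the Part B sample size was chosen mainly to protect the accuracy of the No-Go decision, and Section 4.5 lists a planned futility analysis among the reasons to terminate the study.

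There is a smaller second effect. PFS is derived from scan dates (Section 9.4.2.2), so a scheduled scan that slides with the dose can record progression later than it would have done on the calendar.

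**Working it through.** **1. The plan's own figure.** The synopsis says "eligible participants will receive sabestomig every 3 weeks (Q3W) administered via intravenous infusion", so Cycle c Day 1 = 1 + 21(c − 1).
- Cycle 3 Day 1 = 1 + 42 = Day 43. The scan window opens on Day 43 + 10 = Day 53.
- Cycle 4 Day 1 = Day 64, so the window closes on Day 63.
- Ten weeks after first dose = Day 1 + 70 = Day 71.

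Without delay, the Cycle 3 window closes 8 days before entry. The 10-week figure is consistent with its stated purpose.

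**2. Effect of a delay.** Let d be the cumulative delay in days before the Cycle 3 infusion. The window becomes Day 53 + d to Day 63 + d.
- Not yet open at entry: 53 + d > 71, so d ≥ 19.
- Not yet closed at entry: 63 + d > 71, so d ≥ 9.
- One missed cycle (d = 21): Days 74 to 84.
- A 12-week gap between the Cycle 2 and Cycle 3 doses: Cycle 3 on Day 22 + 84 = Day 106, so d = 106 − 43 = 63 and the window is Days 116 to 126.

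**3. Can such delays occur under the plan?** Appendix I describes steroid tapers of at least 28 days. For several Grade 2 reactions, including pneumonitis and diarrhea/colitis, dosing resumes only after the taper. If Cycle 2 moves 28 days, from Day 22 to Day 50, Cycle 3 falls on Day 71 and its scan on Days 81 to 91. The documents give no expected rate of such holds.

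**4. Sensitivity to the redacted cycle.** Cycle 3 is named only in the change log, which does not call it the first scan. If the first scan is in Cycle 2 (Days 32 to 42), d must be at least 40. If it is in Cycle 4 (Days 74 to 84), even undelayed participants enter before it.

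**5. Illustration for Cohort B1.** The rule comes from Section 9.5.1 and the note to Table 22: Beta(1,1) prior, target 40%, No-Go if P(ORR > 40%) < 10%, futility if the predictive probability of No-Go exceeds 95%. Look size, final N and the number unscanned are assumptions.
- Final boundary R: the largest x with P(ORR > 0.40) < 0.10 under Beta(1 + x, 1 + N − x). This gives R = 11, 19, 26 and 33 for N = 40, 60, 80 and 100.
- At a look of 20 with x responders, future responders k follow a beta-binomial(N − 20; 1 + x, 21 − x). Futility needs P(x + k ≤ R) > 0.95. The boundary is x ≤ 3 for all four values of N.
- True ORR 40%, all 20 scanned: P(X ≤ 3), X ~ Bin(20, 0.40), = 1.6%.
- Two of the 20 unscanned and counted as non-responders: P(X ≤ 3), X ~ Bin(18, 0.40), = 3.3%.

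A range, letting each participant be unscanned with probability u, so that X ~ Bin(n, p(1 − u)):

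| Assumed look and N | True ORR | u = 0 | u = 5% | u = 10% |
|---|---|---|---|---|
| n = 20, N = 40 to 100 (≤ 3) | 40% | 1.6% | 2.5% | 3.7% |
| n = 40, N = 80 or 100 (≤ 9) | 40% | 1.6% | 2.9% | 5.0% |
| n = 40, N = 60 (≤ 10) | 40% | 3.5% | 6.0% | 9.7% |
| n = 20, N = 40 to 100 (≤ 3) | 50% | 0.1% | 0.3% | 0.5% |

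**The case against.** The case on the other side has real force.

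- **Redaction and wording.** The scan cycles are blacked out. Read alone, footnote b permits a scan during a hold, since the only conditions are 10 days after one infusion and before the next. This stands as a limit. But the schedule rows attach the scan to a given cycle's infusion, so a site following them waits for that infusion.
- **Most holds do no harm.** A reader might infer that anyone held for a Grade 2 immune-mediated event cannot be scanned by week 10. The documents do not support that. With a 28-day hold starting on Day 12, Cycle 2 is given on Day 40 and Cycle 3 on Day 61, and the scan opens on Day 71, just in time. A hold that starts after the Cycle 3 infusion leaves the scan due from Day 53. Appendix I also does not hold every Grade 2 event, and its liver rules resume at a low steroid dose rather than after a full taper.
- **Size.** Ten weeks is a minimum, so only the newest participants in a look are exposed. Cohort B1 looks also include earlier Part A participants treated at the RP2D. Four unscanned of 20 would give 6.5%, but nothing in the documents supports that count.
- **Non-responder status is inferred.** SAP Section 4.2.2.1 counts as non-responders those who leave the study or start other therapy before assessment. It is silent on ongoing, unscanned participants. The inference follows from the set definition, and the silence leaves the analyst without a rule.
- **Non-binding rule.** Stopping is at the sponsor's discretion (Section 9.5), and later looks include the late scans. This stands and limits the harm.
- **Duration endpoints.** A reader might also infer that DoR and the 12- and 24-month landmarks are inflated. That is not established. A late first scan also starts the DoR clock late, and the landmarks lie near scans dated from first dose. For PFS, unscheduled imaging is allowed at any time and clinical progression counts (Section 8.1).

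**Conclusion.** The mismatch holds on the current text. Provided the Cycle 3 assessment is the first scan, a cumulative delay of about 19 days or more before the Cycle 3 infusion places a participant in the futility denominator before a scan is due, and no section covers this.

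The statistical effect is a modest push towards false futility. In the illustration it takes the crossing probability from 1.6% to 3.3% at one look, on an assumed look size and number unscanned. It is not evidence that the looks will stop an active drug: the rule is non-binding, the share of participants affected is unknown, and the effect fades as late scans arrive.

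PFS may be lengthened modestly where scheduled scans slide with dosing, within the bound set by unscheduled imaging and the fixed Year 1 scan. No claim is made about bias in DoR or the landmark estimates. The point deserves correction because the change is cheap and bears directly on a decision input.

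**What to change.** 1. In Protocol Tables 2, 3, 4 and 16, state that when dosing is delayed, first-year scans keep the calendar timepoints of the undelayed schedule counted from first dose, with a window and still at least 10 days after the last infusion. This extends to holds the rule that Section 8.1.2 already applies after discontinuation.
2. In Protocol Table 21 and SAP Table 1, include a participant in the interim response-evaluable set only if first dose was at least 10 weeks before cut-off **and** the participant has a post-baseline assessment or has progressed, died, discontinued or started new therapy. Report at each look how many ongoing, unscanned participants are left out.

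The second change alone settles the futility denominator. The first also keeps progression dates on the calendar and leaves few participants for the second to exclude.

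The cost is amendment wording and one analysis-set sentence, with no additional scheduled scans. An occasional scan will fall during a hold, and a few participants will enter a look later. The interim set will depend slightly on follow-up status, because it keeps those who progress or leave and omits ongoing unscanned participants; the reported count makes that visible. No change to dosing or toxicity management is proposed.
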